### ***AF severity assessment***

The patient-reported AF6 questionnaire includes six items (breathing difficulties at rest and upon exertion, limitations in day-to-day life, feeling of discomfort, tiredness and worry/anxiety due to AF) and a score of 0 (no symptoms) to 10 (severe symptoms) is reported for each item, and all scores are added into a single sum score. Sum scores range from 0 to 60, with higher values reflecting more severe AF-related symptoms. The AF6 includes a recall period of the last 7 days(32, 33).

The physician-assessed modified European Heart Rhythm Association symptoms scale is used for symptom severity assessment in patients with AF, relating specifically to the time when patients feel symptoms of AF. Patients in class I are considered to have no symptoms, in class IIa mild, class IIb moderate, class III severe and in class IV disabling symptoms of AF(8, 34).

### ***Health-related quality of life***

The patient-reported SF-36 has a recall period of four weeks and consists of 36 items assessing eight domains ranging from 0 to 100, with higher values indicating better health-related quality of life. The eight domains generate two summary measures: the physical component summary and the mental component summary scores, which will be used to assess health-related quality of life(35).

### **Control group**

Sex and age-matched controls will be recruited by advertisement. The same blood samples will be obtained from controls as on patients with AF but only once, and controls will be asked to complete the SF-36 questionnaire and a questionnaire about previous and current diseases and current medication.

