### **Subject inclusion criteria**

Consecutive study participants will be recruited from the waiting list of all patients planned for AF ablation (pulmonary vein isolation) in Örebro University Hospital. Only patients with symptomatic AF are planned for AF ablation.

Further inclusion criteria:

- Male or female subject  $\geq$  20 years and  $\leq$  75 years
- Paroxysmal AF (AF that terminates spontaneously or with intervention within 7 days (8))
- Written informed consent

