### **Subject exclusion criteria**

- Persistent AF (AF that is continuously sustained beyond 7 days, including episodes terminated by cardioversion after  $\geq$  7 days(8))

- Previous pulmonary vein isolation
- Cognitive or psychiatric condition
- Diabetes mellitus
- Ischemic heart disease
- Heart failure
- Asthma
- Pregnancy
- Previous/current drug or alcohol abuse
- Previous neurological or concomitant musculoskeletal disorders
- Continuous analgesic medication

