### ***Guidelines for obtaining informed consent***

Subjects will enter the study after signing the informed consent form. Candidate participants will receive written information of the study, and oral information by a physician participating in the study. The subjects will be given time to think through participation in the study and to ask questions. Informed consent will be obtained by a Good Clinical Practice qualified physician participating in the study.

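### No sentence applies the exclusion criteria to the controls, so primary objective (2) may compare groups with unequal eligibility by an unadjusted t-test

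*Combined protocol and SAP*

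**What the plan says.** For controls, the Control group section gives the only recruitment rule: "Sex and age-matched controls will be recruited by advertisement". The Abstract (Objective and methods) and the Purpose describe them as age- and sex-matched and without AF, and the Abstract plans 100 of them against 100 patients. Controls also complete "a questionnaire about previous and current diseases and current medication", but no use of the answers for eligibility or analysis is stated.

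For patients, the inclusion section begins "Consecutive study participants will be recruited from the waiting list of all patients planned for AF ablation", adds "Only patients with symptomatic AF are planned for AF ablation", and requires paroxysmal AF. The list under "Subject exclusion criteria" then has 11 items, among them "Previous neurological or concomitant musculoskeletal disorders" and "Continuous analgesic medication".

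Primary objective (2), under Primary endpoint, is the difference in marker levels between patients with symptomatic AF and participants without AF. The Statistical analysis section compares the two groups by an independent t-test. The regression in the same section has age, sex and symptoms as explanatory variables.

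**The concern.** A patient-control difference can be attributed to AF only if the groups are otherwise comparable on what moves the markers. The Abstract describes the markers as linked to the generation or maintenance of chronic pain. The exclusion list removes patients with conditions plausibly tied to such markers, and those on continuous pain medication. If controls are not held to the same list, a difference that is found, or one that is missed, could partly reflect who was allowed into each group. Matching deals with age and sex only, and the t-test adjusts for nothing. The second hypothesis would read higher levels in patients as further proof of central sensitisation in AF, so the inference rests directly on this comparison.

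**Working it through.** **1. Does the list reach the controls?** The passages point both ways.

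- Towards patients only: the paired inclusion criteria, also headed with the word subject, start from the ablation waiting list and require paroxysmal AF, which no control can meet. Two exclusions (persistent AF and previous pulmonary vein isolation) are specific to AF. Controls have their own later section, which does not refer back to the list.
- Towards everyone: the Statistical analysis section calls the comparison group control subjects. The consent guidelines say "Subjects will enter the study after signing the informed consent form", which reads naturally as covering all participants. The other 11 − 2 = 9 exclusions could apply to anyone.

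Neither reading is decisive, and no sentence settles it.

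**2. Does the analysis repair it?** The t-test has no covariates. The regression has no group, comorbidity or medication term, and its symptom variable comes from AF scales described for patients only. It is not an adjusted group comparison.

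**3. How large could a bias be?** The plan gives no effect size, SD, alpha or power, so there is no stated figure to reproduce. Only n = 100 per group comes from the documents. What follows is illustration.

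Assume two-sided 5%, a true difference of 0.40 SD, a share q of controls who would fail an exclusion, and a mean marker shift of delta SD in those controls. Then:

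- observed difference = 0.40 − q × delta
- standard error = √(1/100 + 1/100) = 0.141 SD
- power from the noncentral t with 198 degrees of freedom; with no bias it is 80.4%

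| q | delta (SD) | Bias, −q × delta (SD) | Observed difference (SD) | Power | False-positive rate if the true difference is 0 |
|---|---|---|---|---|---|
| 0.1 | +0.3 | −0.03 | 0.37 | 74.0% | 5.5% |
| 0.1 | −0.3 | +0.03 | 0.43 | 85.7% | 5.5% |
| 0.2 | +0.5 | −0.10 | 0.30 | 56.0% | 10.8% |
| 0.2 | −0.5 | +0.10 | 0.50 | 94.0% | 10.8% |
| 0.3 | +0.5 | −0.15 | 0.25 | 42% | 18.4% |
| 0.3 | −0.5 | +0.15 | 0.55 | 97.2% | 18.4% |

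The higher power in the negative-delta rows is not a gain, because it comes from an inflated difference. Under no true difference, false results are mostly lower-in-AF when delta is positive and higher-in-AF when it is negative. Adding the mixture variance q(1 − q)delta² to the control group changes each figure by less than one percentage point.

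**4. Restriction or adjustment if ineligible controls are already sampled?** Let z = 1 for a control with any excluded condition and 0 otherwise. It is 0 for every patient. Fitting level = a + b × group + c × z gives each of the three cells its own mean, so b is exactly the patient mean minus the eligible-control mean. That is the restricted estimate; only the standard error can differ. Several separate condition terms would add an additivity assumption.

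**The case against.** The strongest reply is that this is a drafting ambiguity. The protocol writes patients and controls when it wants to separate the groups, and calls the controls subjects in the analysis section, so the exclusion list may always have been meant for both. Disease and medication data are planned in both groups, so an imbalance could be described, restricted or adjusted for with little or no new data. The power figures rest on assumed inputs, and the mildest case is small.

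Much of this stands. A reader might infer that the authors chose unequal eligibility, but no passage shows that. A reader might also infer that controls with painful conditions would have higher markers and so mask a real difference. The documents give no blood levels in people with the excluded conditions, and the sign could be the opposite. Nothing in the documents favours any row of the table.

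What does not stand is that the point is only wording. Usage of the word subject is mixed, the inclusion section is plainly about patients, and a team following the Control group section as written would enrol unscreened controls for a primary comparison. Collecting the questionnaire does not protect that comparison unless its use is specified.

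**Conclusion.** The point holds in conditional form and should be fixed. As written, controls need only be age- and sex-matched, without AF and recruited by advertisement, and primary objective (2) is tested without adjustment against patients screened on nine further conditions. If the exclusions were meant for controls, one sentence settles it. If not, the comparison is open to a bias whose sign and size the documents do not allow anyone to determine. The illustrative figures are conditional on assumed values of alpha, effect size, q and delta, and should not be read as expected consequences. Objective (1) is unaffected.

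It would be tempting to say that the change can certainly be made before recruitment, because the protocol describes itself as awaiting ethical approval. That text does not show whether recruitment has since begun, so both situations need an answer.

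**What to change.** In the Control group section, state that the nine exclusions not specific to AF apply to controls. Use the planned disease and medication questionnaire to screen before blood is drawn, adding items on pregnancy and on drug or alcohol abuse if it lacks them. Replace ineligible responders with age- and sex-matched ones. The age range needs no separate rule, since matching to patients already covers it.

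If ineligible controls have already been sampled, base the primary comparison on eligible controls. A single any-excluded-condition indicator gives the same point estimate. Recheck age and sex balance, and report all controls as a sensitivity analysis.

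The cost is one or two sentences and more screening. If 20% to 30% of responders fail (assumed), 100 controls need 100/0.8 = 125 to 100/0.7 = 143 responders. If ineligible controls are dropped and not replaced, 80 or 70 remain. The standard error rises from 0.141 to √(1/100 + 1/80) = 0.150 or √(1/100 + 1/70) = 0.156 SD, and power at the assumed 0.40 SD falls from 80.4% to 75.6% or 72.3%.

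The change does not remove self-selection of volunteers through advertisement, or differences in medication other than continuous analgesics.

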### **Follow-up**

No follow-up visits are scheduled.

### **Primary endpoint**

The primary objectives are (1) to study the association of biomarkers and epigenetic markers and the severity of AF symptoms, and (2) to assess differences in the levels of biomarkers and epigenetic markers in patients with symptomatic AF compared with participants without AF.

### **Secondary endpoint**

Secondary objectives are to study the association of age, sex, AF duration, health-related quality of life, and biomarkers and epigenetic markers.

### **Ethics approval**

The study protocol is submitted to the Swedish Ethical Review Authority for approval.

### **Statistics and data management**

Data collected during the study will be coded.

### ***Statistical analysis***

Data will be presented as mean and standard deviation. Independent t-test will be used to compare biomarkers and epigenetic markers in AF patients and control subjects. Pearson correlations will be used for linear estimates and Spearman's correlations for non-linear parameters. Multiple linear regression analysis will be performed to show associations between explanatory variables (age, sex, symptoms) and biomarkers and epigenetic markers associated with pain. Analyses will be performed using IBM SPSS Statistics 22 (Armonk, NY, USA) or STATA release 14 (College Station, TX, USA).

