### **Purpose**

To study levels of biomarkers and epigenetic markers associated with pain as well as cardiac and inflammatory biomarkers in patients with symptomatic paroxysmal AF, in relation to severity of AF symptoms, and compared to age- and sex-matched controls without AF.

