### ***Blood samples***

Blood samples for biomarkers and epigenetic markers associated with pain, cardiac biomarkers, and inflammatory markers, will be obtained when standard blood samples are taken the day before the ablation, and the day after ablation. In total 30 ml of blood per time will be obtained. In controls, the same blood samples will be obtained once only. Blood

samples will be stored in a biobank for possible later analysis. Blood samples may be analysed in another laboratory in Sweden or in the EU/ESS.

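### Primary objective 2 compares age- and sex-matched groups with an unadjusted t-test; a linear model with group, age and sex would be at least as good and costs almost nothing

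*Combined protocol and SAP*

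**What the plan says.** The Purpose section describes the study as one of patients with symptomatic paroxysmal AF "in relation to severity of AF symptoms, and compared to age- and sex-matched controls without AF". The abstract (Objective and methods) gives 100 patients and 100 controls. The Control group section says only "Sex and age-matched controls will be recruited by advertisement"; it does not say whether matching is individual or by frequency, and gives no age tolerance.

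The second primary objective, in the Primary endpoint section, is "2) to assess differences in the levels of biomarkers and epigenetic markers in patients with symptomatic AF compared with participants without AF". The Statistical analysis section assigns it one test: "Independent t-test will be used to compare biomarkers and epigenetic markers in AF patients and control subjects".

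The same section plans a multiple linear regression to show "associations between explanatory variables (age, sex, symptoms) and biomarkers and epigenetic markers associated with pain". The Secondary endpoint section plans to "study the association of age, sex, AF duration, health-related quality of life, and biomarkers and epigenetic markers". So the plan itself treats age and sex as possible determinants of the markers.

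**The concern.** Matching on age and sex makes the two groups alike on those factors. The independent t-test then computes its standard error as if the groups had been drawn independently, so marker variation due to age and sex stays in the error term although the design has removed it from the difference. The interval is too wide and power is lost wherever age or sex matters for a marker.

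The planned regression cannot stand in for the group comparison. Its listed terms are age, sex and symptoms, with no term for patient versus control. For controls, the Control group section says that "controls will be asked to complete the SF-36 questionnaire and a questionnaire about previous and current diseases and current medication"; the AF6 and the modified EHRA scale are described for patients only (Patient consent and inclusion; AF severity assessment). As written, the regression serves primary objective 1.

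The silence on matching method raises a second issue. Patients may be 20 to 75 years old and controls come from advertisement. If matching turns out loose, the t-test leaves the remaining age and sex imbalance uncorrected, and the estimate can be biased in either direction.

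**Working it through.** **Inputs from the documents.** 100 patients and 100 controls; matching on age and sex; independent t-test.

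**Assumptions, because the documents give no figure.** Two-sided 5% level; true difference 0.4 SD; R² (share of within-group marker variance explained by age and sex) of 0, 0.1, 0.3 or 0.5; age SD 10 years; no dropout. The plan contains no power calculation, so there is no stated figure to reproduce first.

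**Unadjusted baseline.** The standard error of the difference is √(2/100) = 0.1414 SD. The critical t value on 198 degrees of freedom is 1.972, so the half-width of the interval is 1.972 × 0.1414 = 0.279 SD.

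**Close matching.** The true standard error is 0.1414 × √(1 − R²), but the t-test still uses 0.1414. Hence:

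- excess interval width = 1/√(1 − R²) − 1
- n per group at which the t-test's nominal interval would be as narrow as the adjusted one = 100/(1 − R²)
- actual type I error of the t-test = 2 × [1 − Φ(1.972/√(1 − R²))]
- power of the t-test = Φ[(0.4/0.1414 − 1.972)/√(1 − R²)] = Φ[0.856/√(1 − R²)]
- power of the adjusted model: noncentral t on 196 degrees of freedom, noncentrality 0.4 × √50/√(1 − R²)

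| R² | Excess width | Equivalent n per group | Type I error, t-test | Power, t-test | Power, adjusted |
|---|---|---|---|---|---|
| 0 | 0% | 100 | 5.0% | 80.4% | 80.4% |
| 0.1 | 5.4% | 111 | 3.8% | 81.7% | 84.3% |
| 0.3 | 19.5% | 143 | 1.8% | 84.7% | 92.0% |
| 0.5 | 41.4% | 200 | 0.5% | 88.7% | 97.8% |

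The power gain is therefore about 0, 3, 7 and 9 percentage points. Simulation of 100 exactly matched pairs (20,000 runs, age and sex both in the model) agrees: at R² = 0.3, power is 84.3% against 91.8%, and type I error 1.9% against 4.7%. At R² = 0 the adjusted interval is 1.0001 times as wide as the unadjusted one, so the cost of 2 of 198 degrees of freedom is negligible.

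**Pairs matched within ±5 years** (6,000 runs, model with group and age). At R² = 0.1/0.3/0.5, power is 81.6/83.0/87.3% with the t-test and 84.2/91.6/97.6% adjusted.

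**Frequency matching: same age distribution, no pairs** (6,000 runs, same model). The type I error of the t-test is 5.4/5.4/4.9%. Power is 81.0/80.5/80.6% against 84.3/91.6/97.8% adjusted.

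**Loose matching, no true difference.** Let age carry all of R² and let the group means differ by a fixed number of years. The bias of the t-test is √R² × gap/10. For R² = 0.3 and a gap of 2 years this is 0.548 × 0.2 = 0.110 SD.

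| Mean age gap | R² = 0.1: bias (SD) | t-test type I | adjusted type I | R² = 0.3: bias (SD) | t-test type I | adjusted type I |
|---|---|---|---|---|---|---|
| 1 year | 0.032 | 4.3% | 4.8% | 0.055 | 3.2% | 4.6% |
| 2 years | 0.063 | 6.0% | 4.9% | 0.110 | 7.9% | 5.5% |
| 3 years | 0.095 | 8.6% | 4.8% | 0.164 | 16.7% | 4.7% |

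At a 1-year gap the conservatism still outweighs the bias; from 2 years the bias dominates.

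**The case against.** The strongest reply is that the planned test is not wrong. In a study described as matched, the t-test keeps its false-positive rate at or below 5%, so this is a preference about efficiency. The gain depends on an R² that the documents do not give; listing age and sex as a question to study is not evidence that they predict the markers. At R² of 0.1 or less the gain is about 3 points of power at most. The equivalent sample sizes also look larger than the power gains, because the actual power of the t-test rises under matching too. All of this stands, and R² = 0.5 should be read as an upper extreme.

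The loose-matching figures also rest on an assumed age shift. With an age SD of 10 years, the standard error of a mean age difference between two unmatched samples of 100 is 10 × √(2/100) = 1.41 years. A 3-year gap is 3/1.41 = 2.1 standard errors, which chance alone would produce in fewer than 5% of unmatched samples from one population. The 17% figure thus describes matching that has failed. That stands too, though volunteers answering an advertisement need not come from the same age distribution as ablation patients.

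The regression is not expressly limited to patients, and its symptom variable is not defined. That controls cannot enter it is an inference, but it is the natural one, and no patient/control term is listed in any case.

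Finally, adjusting for age and sex does nothing about other differences between ablation patients and volunteers, such as disease or medication. That is correct, and the proposal does not claim otherwise. None of these replies gives a reason to prefer the t-test: the adjusted model does at least as well in every scenario, apart from a negligible cost at R² = 0.

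**Conclusion.** The point holds. The sole planned test of primary objective 2 leaves out the two factors on which the groups are matched, and nothing elsewhere in the plan makes up for it.

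With close matching the cost is precision only: intervals 0 to 20% too wide and 0 to 7 points of power lost for R² between 0 and 0.3, with false positives not inflated. With loose matching, bias is added and false positives can exceed 5%. The size will differ by marker and rests on the assumed R², a difference of 0.4 SD, an age SD of 10 years and, for the loose case, the assumed age gap with age carrying all of R². It is small if R² is 0.1 or less and matching is close.

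This is a change the sponsor should make because it is nearly free. It does not mean that the planned comparison would be invalid.

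**What to change.** In the Statistical analysis section, replace the t-test sentence with:

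> Pre-ablation marker levels in patients will be compared with marker levels in controls by linear regression with group, age and sex as terms.

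The model suits both individual and frequency matching, so the sponsor need not settle the matching method first, although stating it in the Control group section would help the reader. The word pre-ablation is there because patients' samples "will be obtained when standard blood samples are taken the day before the ablation, and the day after ablation" while controls are sampled once; it only writes down the natural reading.

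The cost is one sentence of analysis text. Group, age and sex must already be known for every participant in order to match, so no new data, visits or participants are needed. Fixing the adjustment in advance also removes a choice that could otherwise be made after seeing the data.

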### **Objective and methods**

To study levels of biomarkers and epigenetic markers in blood in patients with symptomatic paroxysmal AF (n=100), in relation to severity of AF symptoms, and compared to age- and sex-matched controls without AF (n=100). Blood will be obtained before and after AF ablation and levels of biomarkers, epigenetic markers and cardiac and inflammatory markers, analysed. Patients will complete an AF-specific symptom and a generic health-related quality of life questionnaire.

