### **Biomarkers**

Biomarkers associated with chronic pain, such as nerve growth factor (NGF), are proteins fundamental during embryonal development for the growth, differentiation, and survival of sensory and sympathetic afferent neurons. During adulthood, they have been found to play a key role in the modulation of nociception through short- (direct sensitisation of peripheral nociceptors) and long-term (changes of gene expression in the dorsal root ganglion) effects. These modifications lead to a wider input from peripheral nociceptors resulting in increased signaling to the central nervous system(27), (28). AF ablation has been shown to increase the plasma level of NGF in humans in the days following the procedure(29), and chronic high

levels of NGF and noradrenaline increased the incidence of inducible AF and its duration in animal studies(30). The use of monoclonal NGF antibodies has been administered to patients with osteoarthritis, providing a significantly greater pain relief compared to NSAIDs and opioids(31).

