### **Epigenetic markers**

Epigenetic mechanisms such as DNA methylation, covalent histone modifications, and non-coding RNAs, have been observed to play an important role as mediators of long-term changes in central and peripheral nervous systems in chronic pain. Epigenetic markers can be measured in blood or tissue(36-37). To our knowledge, pain-related epigenetic markers have not been analysed in patients with AF.

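### Does the plan need to fix a log scale or a rank-based check for the marker comparisons, given that it names only a t-test and linear regression?

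*Combined protocol and SAP*

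**What the plan says.** The Statistical analysis section is the only statistical text in the document. It says "Data will be presented as mean and standard deviation", and names the group test: "Independent t-test will be used to compare biomarkers and epigenetic markers in AF patients and control subjects". Pearson correlations are for linear estimates, with Spearman's "correlations for non-linear parameters", a term the plan does not define. For the regression it says "Multiple linear regression analysis will be performed to show associations between explanatory variables (age, sex, symptoms) and biomarkers" and epigenetic markers.

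The t-test is the only method named for the second primary objective, which is "to assess differences in the levels of biomarkers and epigenetic markers in patients with symptomatic AF compared with participants without AF". The first primary objective, the association of markers with symptom severity, rests on the correlations and the regression.

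The markers are of several kinds. The Biomarkers section says: "Biomarkers associated with chronic pain, such as nerve growth factor (NGF), are proteins". The Epigenetic markers section lists "Epigenetic mechanisms such as DNA methylation, covalent histone modifications, and non-coding RNAs". The Purpose adds cardiac and inflammatory markers. No assay, unit, SD, coefficient of variation (CV) or detection limit is given for any of them.

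**The concern.** Reporting the mean and SD suggests the raw scale without saying so. Protein concentrations are positive and can have a long upper tail. A few high values then inflate the SD, and a t-test or least-squares fit on raw values can miss a real difference. Both primary objectives would be affected, and the one rank method named is offered only for correlations. One unstated scale also has to serve both concentrations and bounded quantities such as methylation proportions.

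What is at stake is mainly power. If the scale were chosen after the results were seen, some control of false positives would be at stake too.

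**Working it through.** **Inputs.** The abstract (Objective and methods) gives 100 patients and 100 controls. The documents give no alpha, power, effect size or marker SD, so there is no figure of the plan's to reproduce. Assumed here: two-sided 5%, and an effect with 80% power on the scale where the marker is normal. The power figures come from simulation with 20,000 runs per case.

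**Size of the assumed effect.** The normal approximation gives d = (1.960 + 0.842) × √(2/100) = 0.396 SD; allowing for the t distribution, 0.398 SD. For a correlation in 100 patients, r = tanh(2.802/√97) = 0.277.

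**Case A: log-normal marker, equal log-scale SD s in both groups.** The ratio of geometric means is g = exp(0.398 s). On the raw scale the standardised difference is

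D = (g − 1) / √[(exp(s²) − 1)(1 + g²)/2].

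- s = 0.5: g = 1.220, D = 0.220/√(0.284 × 2.489/2) = 0.370. Approximate power is Φ(0.370 × √50 − 1.96) = Φ(0.66), about 75%.
- s = 1.0: g = 1.489, D = 0.489/√(1.718 × 3.217/2) = 0.294. Approximate power is Φ(0.12), about 55%.

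The approximation is too low for wide spreads, because most samples from a long-tailed distribution show an SD below the true one. Simulation gives:

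| Log-scale SD | CV | Raw t | Log t | Mann-Whitney | Raw t, type I error |
|---|---|---|---|---|---|
| 0.5 | 0.53 | 75% | 80% | 78% | about 5% |
| 1.0 | 1.31 | 60% | 80% | 78% | 4.5–4.8% |
| 1.5 | 2.91 | 42% | 80% | 78% | 3.5–3.9% |

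The regression with age and sex (n = 100) behaves alike: 75%, 61% and 46% raw, against about 80% logged. To regain 80% with the raw t-test takes about 114, 162–165 and 300 per group.

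**Case B: other shapes, same group sizes.**

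| Marker | Raw t | Log t | Mann-Whitney |
|---|---|---|---|
| Gamma, skewness 1.0, mean up by 0.4 control SD | 72% | 67% | 68% |
| Gamma, skewness 2.0, mean up by 0.4 control SD | 65% | 46% | 54% |
| Log-normal s = 0.5, threefold rise in 15% of patients | 75% | 52% | 36% |

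The differences between raw and log are 72 − 67 = 5, 65 − 46 = 19 and 75 − 52 = 23 points, all in favour of the planned test. For a normal marker with CV 0.33 to 0.40, logging costs about 4 to 10 points, depending on how near-zero values are handled.

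**Case C: unequal spread.** The two scales test different hypotheses. With equal arithmetic means and log-scale SDs of 0.5 and 1.0, the raw t-test rejects in about 7% of runs and the log t-test in 92%. With equal geometric means and the same spreads, the raw test rejects in 72% and the log test in 5%. For SDs of 1.0 and 1.5 with equal arithmetic means, the raw test rejects in about 8%.

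**The case for a change.** The strongest argument for a change is that an open scale is an open choice. In null simulations, taking the smaller of the raw and log p-values gives about 7% false positives, and the smallest of raw, log and Mann-Whitney about 8%. Naming the scale in advance removes that, costs only wording, and needs no knowledge of the distribution. At a log-scale SD of 1.0, the raw test also misses about a quarter of the differences the log test would find: (80 − 60)/80 = 25%.

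The first part stands as good practice. It calls for the scale of each marker to be settled before the groups are compared, and an analyst can do that from the assay and the pooled distribution without choosing by p-value. The excess is also limited: 2 to 3 points above 5%, and only if the choice is driven by the result.

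The second part stands only under Case A with wide spread. It does not support a log default. The protocol's own reasoning makes a rise confined to a subset plausible: the first hypothesis has markers increasing with AF severity, and the Introduction says up to one-fourth of patients report severe symptoms. In the subset case above, the log test and the rank check are the weaker tools. Fixed rules for values below a detection limit, or Spearman for every AF6 correlation, have no basis in the documents either. Spearman costs about 4 points against Pearson on a logged marker when AF6 is near normal (76% v 80%).

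The statement that only power is at risk also needs a limit. Case C shows the raw t-test rejecting in 7–8% of runs when arithmetic means are equal but spreads differ. That excess is modest. The log test does not cure it for the same hypothesis.

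**Conclusion.** The omission is real: the section states no scale, distribution check or sensitivity analysis for the t-test or the regression. Its consequence cannot be signed from the documents. For log-normal concentrations the raw scale loses about 5 points of power at log-scale SD 0.5, 20 at 1.0 and 38 at 1.5. For gamma-type skew or a rise in a subset, the raw scale gains about 5 to 23 points. Neither set of figures applies to bounded markers such as methylation proportions. Nor does the second primary objective, which speaks of differences in levels, say whether arithmetic or geometric means are meant.

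With identical distributions in the two groups, the planned t-test has a type I error of about 5% or slightly less. The plan already names a rank method for correlations, and nothing in it forbids logging a marker whose assay calls for it. Choosing each marker's scale, with a check on another scale or on ranks, is ordinary analysis work that depends on assays not yet named. A blanket rule written now would be a trade-off rather than a clear gain, so no amendment is warranted.

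This rests on the assumed two-sided 5% level, an effect set at 80% power, and 100 per group as stated.
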